Secondary Statistical Analyses: All analyses will be performed using SAS software (SAS Institute Inc., Cary, NC). First, linear mixed-effects regression model (or GEE model) will be constructed to examine the study effect on the weight loss over time among the two diet plans, referred to as Model 1. Covariates include gender, diet group (high-protein and standard), time that the measurement is taken, and an interaction between diet plan and time. Models also include the subject-level random effects to account for the correlation between repeated measures at baseline and subsequent follow-up visits occurring at 2 week to 1 month intervals. Next, mixed-effects regression models will be used to evaluate the differences in hormonal patterns among the three diet plans for various hormones of interest (e.g., CCK, GLP-1, etc). Since the hormonal level over time is expected to be nonlinear, the covariates in the model include diet group (normal vs. high-protein), time (in days), and smooth-spline function of time by group interaction. Next, we will also construct linear mixed-effects regression models to examine the study effect on the continuous efficacy variables and safety variables (e.g., vital signs) over time among the three diet plans using PROC MIXED. The continuous efficacy variables include nutritional assessments (FFQ, 3DFR, and Satiety), selected laboratory and biochemical variables (e.g., HbA1c, insulin), body fat, etc. Models include the same fixed effects in Model 1, and the subject-level random effects, which account for the correlation between repeated measures at baseline and pre-defined time points for different variables (e.g.,

baseline and at weeks 2, 4, 6, 8, 12 and 16 for the nutritional assessments). Lastly, generalized linear mixed-effect regressions will be used to model *any* dichotomous and categorical (e.g., severity of adverse events) secondary variables, respectively, in the PROC GLIMMIX or GENMOD. All tests will be two-sided, and significance level is $p < 0.05$.

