Expected Results/Pitfalls/Significance: We do not anticipate problems in conducting the proposed human experimental studies. Our preliminary data indicate that an isocaloric high protein diet is effective at achieving a reduction in BMI in obese subjects. It is therefore likely that the results will parallel those of the preliminary studies due to the long-term study design and larger study population. It is expected that there is inhibition of the release of ghrelin, which will also be reflected through satiety questionnaires which will be performed during the study.

B. Aim 2. Characterize the changes in the fecal microbiome induced by a high protein diet.

Rationale and hypothesis: Based on our preclinical rodent model data, we hypothesize that a high protein diet will shift the composition of the microbiome of obese subjects, including increased *Akkermansia*, and that this will result in an altered metagenome (abundances of bacterial genes).

Study design: This is a randomized study using the same subjects described in Aim 1. Nutritional assessment, physical examination, bioelectrical impedance, laboratories will be performed at baseline, and weeks 2, 4, 6, 8, 12 and 16. Stool samples will be collected on day 3, 7, 14, 17, 21, 28, 42, 56, 84 and 112.

Study timeline: Data collection will be completed at week 16. The stool samples collected during the study period will be used for 16S rRNA sequencing, shotgun metagenomics, and data analysis.

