Fecal sampling: Subjects will be provided with kits for home sampling. The subjects will urinate first then defecate into the Fisherbrand Commode Specimen Collection System. Subjects will use a spoon to transfer freshly defecated feces to a Para-Pak stool collection cup prefilled with 95% ethanol to fix the samples, allowing storage at room temperature for up to 2 weeks. The remaining feces will be frozen. This involves removing the cup from the toilet hat, tightly closing the lid, and transferring the cup to a Ziploc bag for storage in the subject's freezer. Frozen samples will be delivered to the VA clinic during scheduled study visits using a Styrofoam box and frozen packs. Subjects who forget to bring samples will be provided with prepaid envelopes to mail their samples to the coordinator. Samples will be stored at -80°C. Ethanol-fixed and fresh frozen samples give comparable metagenomics results to samples stored in preservatives such as RNALater while minimizing subjects' risk of exposure to toxic chemicals^(70,33).

2.1 Kinetic analysis of shifts in microbial composition in obese subjects (BMI 27-40) on a high protein diet compared to an isocaloric normal protein diet.

Experimental protocol: DNA will be extracted from fecal samples collected in ethanol using the MoBio Powersoil kit. Sequencing of the 254 base pair V4 region of 16S ribosomal DNA will be performed as we previously described using the HiSeq 2500 to a depth of >200,000 reads per sample^(71,34). Microbial diversity will be compared between the two dietary groups at each time point using the Chao1 index, Shannon index, and phylogenetic diversity. Significance will be determined using a two-sided t-test. Microbial composition will be compared across all samples using weighted UniFrac (a phylogenetic distance metric) and principal coordinates analysis. Significance of differences in composition will be determined using Adonis.

Microbial abundance will be compared between baseline data for the two groups to confirm that randomization was effective in abolishing a pre-existing microbial difference between the

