two groups. The data for all time points will then be fitted to a multivariate model under a negative binomial distribution using DESeq2 with diet group, time point, interaction between diet and time point, baseline BMI, age, sex, and smoking status as covariates. This model will be compared to a reduced model that does not include the diet:time point interaction⁽⁷⁰⁾. A likelihood ratio test will be used to identify microbes with differential abundance by diet at time points after baseline. Estimates of significance will be adjusted for multiple hypothesis testing⁽⁷¹⁾. OTUs that are differentially abundant on a HPD will be grouped by hierarchical clustering, which we anticipate will highlight distinct kinetic patterns of microbial change.

Expected results/potential pitfalls: We do not anticipate problems with the collection or transportation of fecal samples to our clinical research unit. We predict that *Akkermansia* will significantly increase on a HPD as was seen in our rodent studies. We further predict that most HPD-responsive microbes will have altered abundance within the first 3 to 7 days as has been observed in other dietary studies^(72,73). We estimate a 20% dropout rate based on our high protein meal replacement study, leaving approximately 80 subjects per group. This compares favorably to published studies reporting dietary effects on the microbiome using sample sizes of 10-15^(72,73,74). We anticipate that a HPD will have a similar magnitude of effect as these previously studied diets and hence we expect to have sufficient numbers to detect compositional differences.

2.2 Identification of metagenes affected by a high protein diet.

Experimental protocol: We will assess the functional consequences of altered microbial composition by sequencing the genes carried by intestinal microbes. Shotgun sequencing of DNA extracted from fecal samples will be performed using the HiSeq 3000 with a target depth of 10 GB data per sample, comparable to the 11.7 GB depth used by the Human Microbiome Project for stool samples⁽⁷⁵⁾. Due to the costs of sequencing at this depth, we will only sequence baseline samples and samples from day 112.

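### Alpha diversity is tested by about 30 separate daily t-tests that use neither baseline diversity nor the repeated samples; the main cost is precision, and no multiplicity control is stated

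*Combined protocol and SAP*

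**What the plan says.** Section 4.B, Aim 2, 2.1 (Experimental protocol) sets the diversity analysis in two sentences: "Microbial diversity will be compared between the two dietary groups at each time point using the Chao1 index, Shannon index, and phylogenetic diversity", then "Significance will be determined using a two-sided t-test". The Aim 2 study design gives the sampling days: "Stool samples will be collected on day 3, 7, 14, 17, 21, 28, 42, 56, 84 and 112". The same ten days appear under Fecal Sampling in Aim 1 and in the Aim 3 study design. All fall after baseline.

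Other parts of the plan bear on these tests:

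- **Baseline stool.** No baseline day is in the list, but the plan relies on such a sample. Study Visits in Aim 1 includes stool collection at week 0. Section 2.1 says "Microbial abundance will be compared between baseline data for the two groups". Section 2.2 says "we will only sequence baseline samples and samples from day 112".
- **Significance level.** The Aim 1 analysis text says "All tests will be two-sided, and significance level is" p < 0.05. Aim 2 states no other level.
- **Multiplicity.** Section 2.1 says "Estimates of significance will be adjusted for multiple hypothesis testing". The sentence comes directly after the DESeq2 likelihood ratio test for individual microbes.
- **Repeated measures.** For the Aim 1 weight model, Secondary Statistical Analyses says "Models also include the subject-level random effects to account for the correlation between repeated measures at baseline and subsequent follow-up visits", and it carries the approach over to other continuous outcomes. The DESeq2 abundance model in 2.1 fits all time points together with a diet-by-time interaction.

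**The concern.** Diversity is measured on the same samples as taxon abundance and on the same subjects as the Aim 1 outcomes, yet it is the outcome analysed one day at a time. Three things follow.

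First, a subject's own starting diversity should predict later diversity. Leaving it out keeps variance in the comparison that the trial could remove at no cost.

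Second, separate daily tests do not combine evidence across days. They also cannot say whether the diet difference changes over time, although the heading of 2.1 presents this as an analysis of kinetics.

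Third, about 30 tests at 0.05, with no main index or day named and no stated control, leave it open how one or several significant results should be read. At stake is the interpretation of a secondary efficacy outcome, since microbiome changes are listed under Secondary Endpoints.

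**Working it through.** **Inputs from the documents.** Three indices; ten post-baseline days; two-sided 0.05 per test; 100 per arm (Study Design) with 20% dropout.

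**Inputs assumed.** The documents give no effect size, SD or correlation for diversity. The 0.35 SD effect, the correlation r between baseline and follow-up, and the correlations over time and between indices are all assumptions. Exchangeable correlation is used throughout.

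**1. The plan's own figure.** 100 × (1 − 0.20) = 80 per arm, as Aim 2 states.

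**2. Number of tests.** 3 × 10 = 30. Expected false positives with no diet effect: 30 × 0.05 = 1.5, whatever the correlation.

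**3. Chance of at least one false positive.** If the tests were independent: 1 − 0.95^30 = 0.785. That is a reference value only, because the tests share subjects and samples. Simulating 30 correlated null statistics (100,000 runs per setting):

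| Correlation over time | Between indices | P(at least one) | Mean number significant when any is |
|---|---|---|---|
| 0.5 | 0.5 | 0.59 | 2.6 |
| 0.7 | 0.7 | 0.41 | 3.6 |
| 0.9 | 0.7 | 0.26 | 5.9 |
| 0.9 | 0.9 | 0.20 | 7.5 |

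As correlation rises, a false positive becomes less likely, but those that occur come in groups.

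**4. Single-day power at 80 per arm.** Power = Φ(d × √(80/2) / √(1 − r²) − 1.96), with d = 0.35:

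- No adjustment: 0.35 × 6.325 = 2.214; Φ(0.254) = 0.60.
- r = 0.5: 2.214 / 0.866 = 2.556; Φ(0.596) = 0.72.
- r = 0.7: 2.214 / 0.714 = 3.100; Φ(1.140) = 0.87.

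**5. Repairing multiplicity alone.** Bonferroni over 30 tests (0.05 / 30 = 0.00167 each) raises the effect detectable with 80% power from about 0.45 SD to about 0.64 SD. That controls error but worsens the precision problem.

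**6. Which overall test.** Let v = (1 + 9r)/10 − r² be the variance of the ten-day mean after baseline adjustment: 0.30 at r = 0.5 and 0.24 at r = 0.7 (correlation over time also set to r).

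- *Sustained 0.35 SD effect.* The average-difference test has power Φ(0.35 × 6.325 / √v − 1.96) = 0.98 to 0.99. The joint test of diet and diet by day (10 degrees of freedom) has noncentrality 40 × 0.35² / v = 16.3 to 20.4. Its large-sample power is about 0.80 to 0.90 at 0.05, and about 0.66 to 0.80 at the strictest Holm step (0.05 / 3).
- *Transient 0.5 SD effect on 3 of 10 days.* The mean effect is 0.15 SD, so the average-difference test has power Φ(0.15 × 6.325 / √v − 1.96) = 0.41 to 0.49. A plain t-test on an affected day has Φ(0.5 × 6.325 − 1.96) = 0.88. The joint test has noncentrality 40 × δ′Σ⁻¹δ = 45 to 74, where δ holds the ten daily effects and Σ is the baseline-adjusted covariance; its power exceeds 0.99.

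The average is better for a sustained shift, but it can miss an early one.

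**The case against.** The strongest reply is that nothing here is invalid. With randomised groups, each t-test is unbiased and holds its 5% level, so baseline adjustment gains efficiency and does not remove bias. That stands.

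A reader might infer from 30 tests that scattered false positives are likely. The documents do not support that. The chance of any false positive falls below one half once both correlations reach about 0.7, and the errors cluster. Nor are both harms at their worst together: if the baseline correlation resembles the correlation over time, high correlation brings the larger power gain and the lower error rate.

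It can also be argued that the plan already covers the point. The multiplicity sentence in 2.1 has no explicit scope, and the Aim 1 mixed models apply to continuous efficacy variables, among which microbiome changes are listed. This is weak. The multiplicity sentence follows the DESeq2 test, the mixed-model text does not name diversity, and 2.1 gives diversity its own, different test. At most the sponsor should state the scope.

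Another objection is that a single average post-baseline difference would suit the question poorly. This stands. Section 2.1 predicts that most responsive microbes will change within 3 to 7 days, and calorie restriction begins at the 2-week visit, so the early samples belong to a different dietary phase. The overall test must be able to see early or transient differences.

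Finally, the consequence is limited. The Aim 2 hypothesis concerns composition, *Akkermansia* and the metagenome, and Aim 3 builds on microbial abundance. This also stands.

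**Conclusion.** The point holds as a matter of efficiency and clarity. The plan specifies about 30 unadjusted t-tests on alpha diversity, ignores baseline diversity and the repeated sampling, and states no multiplicity control for them, although it models other repeated outcomes jointly.

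Under the assumed 0.35 SD effect, baseline adjustment raises single-day power from 60% to 72-87% for r of 0.5 to 0.7. The direction of the gain holds for any positive r; its size is assumed. The familywise error of roughly 20-59% also rests on assumed correlations, whereas the expected count of 1.5 does not.

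All power figures take 80 per arm. The sample size text still carries 55 evaluable per arm, at which the unadjusted detectable effect would be about 0.53 SD.

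It would go too far to infer that the diversity tests are biased, that a false positive is more likely than not, or that the weight result is at risk. Diversity is a secondary outcome and the primary conclusion does not depend on it.

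**What to change.** For each index, replace the daily t-tests with one repeated-measures mixed model that has baseline diversity as a covariate, diet, categorical day, diet by day, and within-subject correlation. Then:

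- Make the formal test a joint test of diet and diet by day, so that both sustained and early or transient differences can be detected.
- Control multiplicity over the three indices, for example with Holm. Unadjusted, three tests carry a familywise error of up to 1 − 0.95³ = 0.143 if independent; Holm holds it at 0.05.
- Report day-specific adjusted differences with confidence intervals.
- State whether the multiplicity sentence in 2.1 applies only to the DESeq2 tests.
- Add the baseline stool sample to the collection days wherever they are listed, because the covariate depends on it and the plan already relies on it.

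The cost is a short rewrite of 2.1 and slightly more analysis work. The mixed-model software is already planned, and no subjects, visits or assays are added. The joint test gives up some power against a purely sustained shift compared with an average-difference test.

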Stool samples will be collected on day 3, 7, 14, 17, 21, 28, 42, 56, 84 and 112. Subjects will be provided with kits for home sampling. The subjects will urinate first then defecate into the Fisherbrand Commode Specimen Collection System. Subjects will use a spoon to transfer freshly defecated feces to a Para-Pak stool collection cup prefilled with 95% ethanol to fix the samples, allowing storage at room temperature for up to 2 weeks. The remaining feces will be frozen. This involves removing the cup from the toilet hat, tightly closing the lid, and transferring the cup to a Ziploc bag for storage in the subject's freezer. Frozen samples will be delivered to the VA clinic during scheduled study visits using a Styrofoam box and frozen packs. Subjects who forget to bring samples will be provided with prepaid envelopes to mail their samples to the coordinator. Samples will be stored at -80°C. Ethanol-fixed and fresh frozen samples give comparable metagenomics results to samples stored in preservatives such as RNALater while minimizing subjects' risk of exposure to toxic chemicals ⁽³³⁾.

Statistical Analysis:

Statistical Design: This is a 2-group randomized nutritional study to evaluate whether the high-protein diet will improve weight loss in comparison to a standard (control) diet. Eligible subjects will be randomly assigned into one of the two groups in a ratio of 1:1.

Sample Size Determination: The sample size is determined based on the Specific Aim 1 to significantly improve weight loss, as observed by comparing the high-protein diet to the standard diet. The primary outcome of interest is weight loss at 16 weeks (the end of the study). An evaluable sample size of at least 165 (i.e., 55 per arm) will achieve 80% power to detect an effect size of 0.245 using an F test with a two-sided 0.05 significance level when comparing each of the two high-protein diets to the standard diet, assuming that the mean weight loss for the standard diet is 14 lbs with the common standard deviation within group of 10 (from preliminary data), and the size of the variation in the means is 2.45. To account for an attrition rate of up to 20%, we will enroll a total of 200 subjects (66 per arm). Preliminary data suggest that the estimated effect size ranges from 0.23-0.34 when comparing the high-protein diet to the standard diet.

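### The Aim 2.1 diet-by-time test has no subject term, so its p-values are miscalibrated if a person's stool samples are positively correlated

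*Combined protocol and SAP*

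**What the plan says.** Section 4.B, Aim 2.1 (Experimental protocol), fits one model per taxon to the pooled 16S data: "The data for all time points will then be fitted to a multivariate model under a negative binomial distribution using DESeq2 with diet group". The remaining terms are time point, then "interaction between diet and time point, baseline BMI, age, sex, and smoking status as covariates". Subject is not on the list.

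The test is defined by what is removed: "This model will be compared to a reduced model that does not include the diet:time point interaction". Its purpose follows: "A likelihood ratio test will be used to identify microbes with differential abundance by diet at time points after baseline".

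The data are repeated measures. The sampling schedule (4.A, Fecal Sampling; repeated under Aims 2 and 3) reads: "Stool samples will be collected on day 3, 7, 14, 17, 21, 28, 42, 56, 84 and 112". That is ten days. A baseline sample is implied, because Aim 2.1 also states: "Microbial abundance will be compared between baseline data for the two groups". Each person can therefore supply up to 11 samples.

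For Aim 1, Secondary Statistical Analyses handles the same feature explicitly: "Models also include the subject-level random effects to account for the correlation between repeated measures". Nothing in Aim 2.1 plays that part.

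**The concern.** All subjects are sampled on the same days, so diet:time compares how people change, not how they differ from one another. A model with no subject term puts stable person-to-person differences into the dispersion. The interaction is then judged against a variance that includes a component which cancels out of it. If the negative binomial is adequate, the test statistic is too small and real diet effects are missed.

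This is the taxon-level test of the plan's second hypothesis, that the diet shifts the microbiome, and it covers the prediction about *Akkermansia*. For the 16S data, Aim 3 (Bioinformatics protocol) carries forward only microbes found enriched or depleted in Aim 2.1. A microbe missed here does not reach the 16S response classifiers. The plan calculates no power for this test; it argues adequacy by comparing its sample size with published studies.

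**Working it through.** **Inputs from the documents.** Planned enrolment is about 100 per arm with 20% dropout: 100 × (1 − 0.20) = 80, which reproduces the plan's "leaving approximately 80 subjects per group". Baseline plus ten listed days gives 11 time points, so diet:time has (2 − 1) × (11 − 1) = 10 degrees of freedom. The nominal level is 5% two-sided, stated for the Aim 1 secondary analyses and used here per taxon before multiplicity adjustment.

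**Assumed.** Within-person correlation ρ = 0.1, 0.2, 0.3, 0.5 (results are in that order throughout), the effect shape, and the count distribution.

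**Step 1: constant correlation, Gaussian approximation on the log scale.** Let total variance be σ². The planned fit uses σ² as error variance, but a within-person contrast has error variance σ²(1 − ρ). The planned statistic is therefore (1 − ρ) times the correct one, and it rejects only when the correct statistic exceeds 18.307/(1 − ρ), where 18.307 is the 5% critical value of χ² on 10 df. A noncentrality of 16.24 gives the correct test 80% power.

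| ρ | 18.307/(1 − ρ) | Actual size | Power (correct test 80%) |
|---|---|---|---|
| 0 | 18.31 | 5% | 80% |
| 0.1 | 20.34 | 2.6% | 72% |
| 0.2 | 22.88 | 1.1% | 61% |
| 0.3 | 26.15 | 0.35% | 46% |
| 0.5 | 36.61 | 0.007% | 13% |

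With only ten time points (9 df), power is 72%, 62%, 48% and 15%. At a per-test threshold of 0.001, to mimic multiplicity adjustment, it is 70%, 56%, 39% and 6%.

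**Step 2: decaying correlation.** Take correlation ρ·exp(−gap/τ) over the actual days, with a sustained shift after baseline that a size-calibrated subject-adjusted test detects with 80% power.

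| τ (days) | Size | Power |
|---|---|---|
| 30 | 4.0 / 3.2 / 2.6 / 1.9% | 77 / 74 / 71 / 65% |
| 60 | 3.5 / 2.4 / 1.6 / 0.8% | 76 / 71 / 65 / 51% |
| 120 | 3.2 / 1.8 / 1.0 / 0.3% | 75 / 67 / 58 / 37% |

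**Step 3: how much of the loss is calibration?** In Step 1 the two statistics differ only by a scale factor, so their size-calibrated power is identical and the whole loss is p-values that are too large. For counts, this was simulated with 80 per arm, 11 samples, mean count 50 and total dispersion 0.5 (both assumed), fixed subject terms, and 600 null and 600 alternative runs. Monte Carlo error is about 2 points, somewhat more for calibrated power.

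| Negative binomial fits | ρ = 0.1 | 0.2 | 0.3 | 0.5 |
|---|---|---|---|---|
| Planned test, nominal 5%: size | 4.0% | 1.7% | 0.7% | 0.2% |
| Planned test, nominal 5%: power | 70% | 65% | 55% | 16% |
| Planned statistic, calibrated to 5%: power | 75% | 81% | 78% | 65% |
| Subject-adjusted, calibrated to 5%: power | 76% | 82% | 85% | 74% |

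Calibration alone recovers 5, 16, 23 and 49 points (row 3 minus row 2). The subject term adds a further 1, 1, 7 and 9 (row 4 minus row 3). A separate run agreed in pattern: about 74%, 64%, 53% and 16% as planned, and 78%, 75%, 76% and 70% once calibrated.

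**Step 4: heavier tails than the negative binomial (lognormal counts).**

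| Log-variance | Size, planned | Size, fixed subject terms | Calibrated power, planned v subject |
|---|---|---|---|
| 0.5 | 15 / 10 / 6 / 1% | 14 / 13 / 11 / 9% | 78 v 85, 77 v 84, 72 v 84, 65 v 75% |
| 1.5 | 61 / 57 / 52 / 33% | 25 / 24 / 22 / 18% | 78 v 96, 68 v 92, 60 v 92, 43 v 86% |

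Here the planned test can be liberal. Adding subject gains 7 to 12 points, or 18 to 43, at matched size, but does not by itself restore 5%.

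**The case against.** The strongest reply is that the missing subject term costs little information. When both tests are held at a true 5% and the negative binomial fits, the gain is 1 to 9 points, and the first two gains (1 point each) are within simulation error. This stands. It limits the claim but does not remove it, because the plan describes no recalibration of the likelihood ratio test.

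Second, the size of the loss depends on inputs that the documents do not give. This stands too. At zero correlation there is no loss, and at 0.1 with 60-day decay 80% power becomes only 76%. Under purely serial correlation with a slowly building effect, a test with unstructured covariance was no better than the planned one (14.8% v 15.4% power at 30-day decay; 19.4% v 23.1% at 7 days). The plan, however, predicts most changes within 3 to 7 days. The simulations also omitted DESeq2's dispersion shrinkage, so exact rates may not carry over.

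Third, the remedy has its own calibration problem. At nominal level, fixed subject terms gave size of 4-8% when the negative binomial fits, 9-14% with moderately heavy tails and 7-25% with very heavy tails, depending on the dispersion estimator. A Gaussian random-intercept test reached 7-12% under pure serial correlation, and the negative binomial mixed model was not simulated. This is why the fix should not rely on the nominal chi-square reference.

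A reader might infer the familiar opposite error: that treating repeated samples as independent inflates false positives. That would apply to a diet main-effect test (33-49% at constant correlations of 0.3 to 0.7), but Aim 2.1 does not test the main effect; it drops only the interaction. Size above 5% arises here from misfit of the count distribution, which is a separate problem.

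**Conclusion.** The point holds conditionally. The listed terms omit subject, the samples are repeated within person, and the tested contrast is within person. With positive within-person correlation, the diet:time p-values are therefore miscalibrated. If the negative binomial fits, they are too large: depending on the assumed correlation, 80% power becomes 72% to 13% when correlation is constant, or 76% to 51% when it decays over about 60 days. If counts are heavier-tailed, the size error can go the other way.

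The documents do not support saying that the test certainly loses power, because they give no within-person correlation. Nor is most of the loss irrecoverable when the negative binomial fits, since calibrating the planned statistic recovers most of it.

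The reach is limited. Microbiome change is a secondary endpoint, and the Adonis and diversity comparisons also bear on the second hypothesis. The shotgun route in Aim 3 does not pass through this test, and the primary weight endpoint is untouched. The change is worth making because it is cheap and because this test selects the 16S microbes for Aim 3. Confidence is moderate.

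**What to change.** For the Aim 2.1 diet:time test only:

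- Include subject in both the full and the reduced model. Either use fixed subject terms nested in diet, which absorb diet and the time-constant covariates, or use a negative binomial mixed model with a subject random intercept.
- Take p-values from permuting diet labels between whole subjects, or use that permutation to recalibrate the statistic, before the multiplicity adjustment. Do not rely on the nominal chi-square reference.
- As an acceptable minimum, keep the planned statistic and permute whole subjects.

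Keep the covariate-only fit, without subject effects, for the Aim 3 residuals. Fixed subject effects would remove the stable between-person differences that Aim 3 relates to response. In an illustration with 80 subjects and an assumed correlation of 0.4 between stable abundance and endpoint, power for the baseline Spearman correlation fell from 32%, 46% and 68% (ρ = 0.2, 0.3, 0.5) to about 5%.

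Cost: SAP wording and computing time, with no new data. There would be two fits per taxon, about 160 subject parameters per taxon if fixed terms are used (2 × 80), and the permutation runs. Without permutation, size can exceed 5% with fixed terms under heavy tails, or with a random intercept under serial correlation.
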